## Healthy Cohort Data Analysis:

#### **Power Statement:**

#### Population Justification:

We have determined that healthy volunteers should be sufficient to validate the metrics of tidal volume and respiratory rate, due largely to the fact that healthy volunteers are able to breathe through a range of respiration rates and tidal volumes without putting their health at risk. Using the intended use population, who are generally ailing, struggling to breathe normally, and elderly, we would likely not be able to cover the full range of measured values with as much standardization as we would like to in this protocol. The mode of operation of the device and its use does not change whether a subject is healthy or part of our intended use population, and thus we believe that whether this data comes from healthy or ill volunteers does not matter in this case.

#### Sample Size Justification:

Based on preliminary tests using publicly available databases and internally collected data, the root mean squared error on respiration rate for our system ranges between 0.5 and 0.8 bpm. For an average respiration rate of 20bpm, this is equivalent to 2.5 to 4% error. We expect the relative error of the tidal volume performance to be similar. For these purposes, we will use a worst-case scenario of a standard deviation of 10%. Using the paired-difference equivalence test power formula, we calculate the number of subjects n needed to demonstrate that the 2 device measurements are equivalent ( $\delta = 0$ ) within 10% (B = 0.10). To obtain a 2-sided alternative with 90% power we set  $z\alpha = 1.96$ , and  $z\beta = 1.65$ . We can then calculate the required n = 13. This suggests that with 13 subjects we would be able to demonstrate equivalence (with 90% power) if the differences in the measurements between the CPM Device and the reference spirometers are within 10%. However, to better reflect a broader patient population and since we might be under-estimating our error, we plan to enroll 20 subjects.

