## **Outcome Measures:**

Primary Outcome Measures

- 1) Accuracy of CPM System calculated RR versus reference device\*
  - Correlation coefficient between reference and test device
  - RMSE accuracy
- 2) Accuracy of CPM System calculated rTV as compared to reference device calculated TV\*
  - Correlation coefficient between reference device and test device within subjects
  - Average correlation coefficients across subjects for rTV for immediate and long timeframes between measurements
- 3) Standard deviation of the difference between reference measured impedance and CPM measured impedance across multiple measurements
- 4) Average of within-subject standard deviation (STD) of TI values from test device for short term measurements

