## **Endpoints**:

- Respiration Rate RMSE < 2 BPM between reference and test device at 8-40 BPM
- Relative Tidal Volume Precision has an  $R^2$  value > 0.5

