## Sample Size Justification:

Based on preliminary data, the standard deviation ( $\sigma$ ) of the thoracic impedance for an individual subject did not exceed 5.1  $\Omega$  when placement was controlled. Using the paired-difference equivalence test power formula, we calculate the number of subjects n needed to demonstrate that the 2 device measurements are equivalent ( $\delta = 0$ ) within 6  $\Omega$  (B = 6). To obtain a 2-sided alternative with 90% power we set  $z\alpha = 1.96$ , and  $z\beta = 1.65$ . We can then calculate the required n = 10. This suggests that with 10 subjects we would be able to demonstrate equivalence (with 90% power) if the differences in the measurements between CPM Device and the reference device are within 6  $\Omega$ . However, we know that our estimates of the standard deviation might be inaccurate since they are based on a small sample of data and did not include the same patient population. To account for that potential error, we plan to enroll 20 subjects.

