# Endpoints

Thoracic Impedance Precision (primary)

- Std < 6 Ohms from measurement to measurement (short term) within a subject
- Std of Z to reference  $X \le 6$  Ohms for short- and long-term measurements
- Respiration Rate Accuracy (secondary)
- RMSE < 2 bpm between reference and test device
- *Tidal Volume Accuracy (secondary)* 
  - $R^2$  value > 0.5

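### The stated 90% power is for a mean-equivalence test that neither cohort's analysis runs, so it gives no assurance on the RMSE, R² and SD endpoints; the impedance sizing uses an individual-subject SD, and averaging within-subject SDs loosens the 6-ohm limit

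*Combined protocol and SAP*

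**What the plan says.** Both cohorts are sized with a power formula for paired-difference equivalence, with a true difference of zero and z-values of 1.96 and 1.65.

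- **Healthy Cohort Data Analysis, Sample Size Justification.** The margin is 10%. For the spread, "we will use a worst-case scenario of a standard deviation of 10" percent. The conclusion is "This suggests that with 13 subjects we would be able to demonstrate equivalence (with 90% power"; 20 are to be enrolled.
- **Pathologic Cohort Data Analysis, Sample Size Justification.** The margin is 6 ohms. The SD "of the thoracic impedance for an individual subject did not exceed 5.1" ohms when placement was controlled. The conclusion is "This suggests that with 10 subjects we would be able to demonstrate equivalence (with 90% power"; again 20 are to be enrolled.

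The success criteria are different quantities. The healthy-cohort Endpoints section requires "Respiration Rate RMSE < 2 BPM between reference and test device at 8-40 BPM" and an R² above 0.5 for relative tidal volume. The pathologic-cohort Endpoints section requires "Std < 6 Ohms from measurement to measurement (short term) within a subject" and an SD to reference of at most 6 ohms over short and long term. Under Outcome Measures, the corresponding primary outcomes are "Standard deviation of the difference between reference measured impedance and CPM measured impedance across multiple measurements" (outcome 3) and "Average of within-subject standard deviation (STD) of TI values from test device for short term measurements" (outcome 4).

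The two Effectiveness and Endpoint Analyses sections plan scatter and Bland-Altman plots, MAE, RMSE, correlations, the SDs of the agreement measures, and R². They contain no equivalence test, no margin on the mean difference, and no confidence bound for any threshold.

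**The concern.** A reader will take 90% as the chance of meeting the endpoints. It concerns only the mean difference. Since RMSE² = bias² + variance of the error, the mean difference can be exactly zero while RMSE or SD is at or beyond its limit. In a study meant to support a 510(k) submission, the stated power then supports a claim that is not tested, and the tested claims have no stated support.

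Two further matters bear on the impedance endpoints. The formula and outcome 3 both need the SD of the CPM-minus-reference difference, but the SD put in describes one subject's impedance readings. And a sample SD from few readings is biased low, so averaging such SDs makes a 6-ohm limit easier to meet than it looks.

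**Working it through.** **1. The plan's figures reproduce.** Formula: n = (zα + zβ)² × SD² / B².

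- Healthy: (1.96 + 1.65)² × (0.10/0.10)² = 13.03; the plan states 13.
- Pathologic: 3.61² × 5.1² / 6² = 9.42; the plan states 10.

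Using 1.65 for zβ is right for 90% power at a true difference of zero, because the type II error is split over two sides. The normal-approximation power, 2Φ(B√n/SD − 1.96) − 1, is 90.0% at n = 13 and 92.2% at n = 10.

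**2. The same mean test with the SD estimated.** Equivalence is declared when |mean difference| + t × s/√n < B, with t the 97.5% point on n − 1 df. Power is 2Φ(√n × (B − t·s/√n)/SD) − 1 averaged over the distribution of s, counting zero where the bracket is negative.

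| Cohort (SD, margin) | n and power |
|---|---|
| Healthy (10%, 10%) | 13: 82%; 15: 89.8%; 16: 92.4%; 20: 97.7% |
| Pathologic (5.1, 6 ohms) | 10: 82%; 11: 87.8%; 12: 91.8%; 20: 99.7% |

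So 90% is first reached at 16 and 12 subjects.

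**3. The SD of the difference.** The documents do not give it. As an assumption only, let both devices have SD 5.1 with correlation r; the SD of the difference is 5.1 × √(2(1 − r)). This gives 3.95 ohms at r = 0.7, 5.1 at r = 0.5, and 7.21 at r = 0. Mean-test power at n = 20 is then above 99.9%, 99.7% and 88%. It falls to 90% at about 7.06 ohms. The value could therefore lie on either side of 5.1.

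**4. Averaging within-subject SDs.** For k independent normal readings, the expected sample SD is c4(k) × the true SD.

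- k = 3: c4 = 0.886, so a limit of 6 acts like 6/0.886 = 6.77 ohms.
- k = 6: c4 = 0.952, so it acts like about 6.31 ohms.

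The study schedule gives three CPM readings per application and six before the one-hour break. The Thoracic Impedance Endpoint Justification derives a required precision of 6.1 ohms before setting 6, so both effective limits exceed that figure.

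Pass rates below 6 ohms for 20 subjects, three readings per SD, by simulation for the average. For the pooled SD they are P(χ² on df < df × 36/SD²), with 40 df for one application and 120 df for three:

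| True SD (ohms) | Average, one / three applications | Pooled, one / three applications |
|---|---|---|
| 5.1 | 99.6% / >99.9% | 95% / 99.7% |
| 6.0 | 86% / 97% | 53% / 52% |
| 6.5 | 65% / 73% | 27% / 12% |
| 7.0 | 40% / 32% | 11% / 1% |

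With six readings averaged, a true SD of 6.0 passes 76% of the time and 6.5 passes 34%.

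**The case against.** The strongest reply is that the plan already absorbs most of this. It raises 13 and 10 to 20, and says the preliminary impedance SD may be inaccurate. At 20 subjects the mean test has ample power on the plan's inputs. That stands: the shortfall at 13 and 10 is an error in a stated figure, not a shortage of subjects. A reader might infer that 20 per cohort is too few; the documents do not support that.

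A reader might also infer that the respiration-rate endpoint is close to a coin toss. With zero bias and a constant error SD of 2 BPM (10% of 20), RMSE < 2 is met 51–54% of the time. That is only an illustration. It takes the plan's deliberate worst case and holds the error at 2 BPM at every rate. A constant 10% error over the 12 items within 8–40 BPM would instead give a true RMSE of about 2.25, if the natural rate is assumed to be 15. At the preliminary RMSE of 0.5–0.8 BPM the endpoint is met more than 99% of the time. Similarly, chances of 99.9%, 88% and 17% of meeting the SD-to-reference limit (at 3.95, 5.1 and 7.21 ohms) assume one difference per subject, whereas the outcome covers multiple measurements. None of these is an estimate of this study's success.

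The averaged SD is a pre-specified outcome, and its bias is modest with more readings. With all nine readings the limit would act like 6.19. But nine is a weak reading of "short term", because the endpoints separate short from long term and the schedule's only break is at one hour. Three or six is a genuine ambiguity.

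**Conclusion.** The point holds in this form. The 90% describes a mean-equivalence test that is not planned and says nothing about the RMSE, R² or SD endpoints. As a statement about the mean test it is also too high at the quoted sizes: about 82% at 13 and at 10, on the plan's inputs with 0.025 per side. The 5.1 ohms is not the SD of the difference. It would be going too far to say that it understates that SD, since variation shared by the devices would lower the SD of the difference and independent errors would raise it.

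The averaged short-term SD loosens the 6-ohm limit to about 6.77 ohms with three readings or 6.31 with six, assuming independent normal readings. With three readings, a device whose true SD lies between 6 and about 6.77 passes more often than not; well above that it usually fails. This should be fixed, but it calls into question neither the sample size nor the thresholds themselves.

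**What to change.** 1. In both Sample Size Justification sections, state that the power concerns mean bias only and does not apply to the RMSE, R² or SD endpoints. Correct the 90% at 13 and 10 subjects to about 82%. Do not print 97.7% or 99.7% as the study's power: that would raise the figure for a test that is not run, and the second rests on the 5.1 ohms. Show any impedance figure at n = 20 over a labelled range of assumed SDs of the difference, such as 99.7% at 5.1 ohms, 90% at about 7.06 and 88% at 7.21.
2. Describe 5.1 ohms as an individual-subject SD.
3. Compute the short-term impedance SD as the square root of the pooled within-subject variance. Fix whether "short term" means the three readings within an application or the six in the first visit.
4. Report each endpoint with a confidence bound that respects clustering by subject, its method and level set in advance. No new pass rule is needed.

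The cost is wording and a short analysis, with no added subjects. The downside falls on pooling: at a true SD of 5.1 ohms with three readings, the pass rate drops from 99.6% to 95% (one application) or from above 99.9% to 99.7% (three).

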#### **Data Analysis Plan:**

#### Demographics:

A table will be constructed with counts and percentages of the number of subjects who were screen failures, the number of subjects enrolled in the study, the number of subjects withdrawn from the study before study completion, and the number who completed the study. For those subjects who withdrew before completion of the study, counts and percentages of the reasons for withdrawal will be tabulated. The continuous demographic characteristics at screening will be summarized for all subjects enrolled in the study using descriptive statistics (mean, standard deviation, median, minimum, maximum, and number of non-missing observations). The categorical baseline characteristics will be summarized for the study participants using frequency counts and percentages.

#### Effectiveness and Endpoint Analyses:

Respiration rate and tidal volumes from the CPM System will be derived from the CPM analytics engine as described previously in the protocol, and the equivalent parameters will be recorded from the reference device output.

For pairs of measurements collected continuously with the CPM and capnography device, scatter plots with the 45-degree line of agreement superimposed will be constructed from paired observations from the two sources along with Bland-Altman plots of the data. The mean absolute error (MAE) and the root-mean-square error (RMSE) estimates of agreement will be calculated for each comparison, as well as correlation coefficients. The standard deviations of each of the agreement measures will also be computed. The R^2 value for the tidal volume measurement will also be calculated.

## **Endpoints**:

- Respiration Rate RMSE < 2 BPM between reference and test device at 8-40 BPM
- Relative Tidal Volume Precision has an  $R^2$  value > 0.5

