## **Objectives:**

Primary Objectives

1) Validate Respiration Rate (RR) accuracy derived by the Cardiopulmonary Management (CPM) System in the range of 6-40 BPM\*

- 2) Validate relative changes in tidal volume (rTV) derived by the CPM System\*
- 3) Validate consistency in measurement-to-measurement and day-to-day changes in median Thoracic Impedance (TI) as well as position-dependent Delta Impedance ( $\Delta Z$ ) derived by the CPM System

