10	15 BPM	Natural (~500mL peak-to-peak)	Patient, App	2 min
11	15 BPM	Shallow breaths (< 500mL p2p)	Patient, App	2 min
12	15 BPM	Deep breaths (> 500 mL p2p)	Patient, App	2 min
13	10 BPM	Extremely deep "yoga" breaths (> 750 mL p2p)	Patient, App	2 min

A single metered breathing app or metronome will be used to pace respiration rates throughout the study. The same breathing measurement method will be used across all patients. It is assumed that actual respiration rates will differ slightly from those described in the protocol. Higher and lower respiration rates may be tailored slightly to accommodate the abilities of participants. During both phases of varying respiration rate (items 1-9 in above table) and varying tidal volume (items 10-13 in above table), both respiration rate and tidal volume will be tracked from the reference device.

Readings will not be considered "successful" or "complete" unless all CPM device errors are resolved prior to the device streaming mode. In the case that a contact or tilt error cannot be resolved, the measurement must be repeated until the data quality is deemed sufficient. If the device begins peeling off of the skin during a measurement (as noted by a participant) and the streaming data quality looks questionable, the measurement must be repeated and the adhesives replaced to ensure good contact. The IFU can be followed for troubleshooting tips regarding issues with data quality. The device may have to be replaced, the skin moisturized, or the adhesive on the device replaced. Any note regarding measurement issues and steps taken to resolve these issues must be noted in the CRF.

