## **Respiration Rate Endpoint Justification**

The Respiration Rate is derived by the CP Analytics Engine from impedance measurements taken by the CPM device for a one (1) minute period. The CP Analytics Engine performs a quality control (QC) check for 30 seconds of consecutive impedance measurement samples. This QC-validated measurement data of 30 seconds results in a maximum computational accuracy of 2 BPM for the respiration rate. Consequently, an accuracy of 2 BPM is deemed sufficient for the CPM Device's intended use.

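### Primary Objective 1 covers 6–40 BPM, but the only healthy-cohort pass rule for respiration rate starts at 8 BPM, so the 6 BPM step has no acceptance limit and no reason is given

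*Combined protocol and SAP*

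**What the plan says.** All references are to the combined protocol and SAP.

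- **Objectives, Primary Objective 1:** "Validate Respiration Rate (RR) accuracy derived by the Cardiopulmonary Management (CPM) System in the range of 6-40 BPM".
- **Outcome Measures, first primary outcome:** "Accuracy of CPM System calculated RR versus reference device", by correlation and RMSE, with neither a range nor a limit.
- **Study Procedures, Healthy Cohort:** the exercise table has 13 items. Item 1 is natural breathing. Items 2–9 are paced at 6, 10, 15, 20, 25, 30, 35 and 40 BPM. Items 10–13 vary tidal volume at 15 or 10 BPM. Slight departures from the paced rates are expected and allowed.
- **Healthy Cohort, Population Justification:** healthy volunteers are used because with patients "we would likely not be able to cover the full range of measured values".
- **Healthy Cohort, Effectiveness and Endpoint Analyses:** MAE and RMSE "estimates of agreement will be calculated for each comparison", with correlations and Bland-Altman plots. No rate range and no pass limit are attached.
- **Healthy Cohort, Endpoints:** "Respiration Rate RMSE < 2 BPM between reference and test device at 8-40 BPM".
- **Respiration Rate Endpoint Justification:** "This QC-validated measurement data of 30 seconds results in a maximum computational accuracy of 2 BPM for the respiration rate". The lower bound of 8 BPM is not mentioned.
- **Pathologic Cohort, Endpoints:** "RMSE < 2 bpm between reference and test device", listed as secondary and without a range.

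**The concern.** The objective and its acceptance criterion have different lower bounds, and the procedure follows the objective. Each healthy subject performs a 6 BPM exercise, yet the criterion excludes that rate. Nothing is paced at 8 BPM, so the lowest paced step that is scored is 10 BPM.

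The Study Design section says the study is meant to ready the device for a 510(k) submission. On the text as it stands, the respiration-rate endpoint could be met and Primary Objective 1 presented as achieved over its full range, although the endpoint says nothing about 6 to below 8 BPM. Disagreement at 6 BPM would appear in the descriptive summaries but would not count against the result.

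**Working it through.** **1. The plan's own figure.** The healthy-cohort Sample Size Justification gives SD = 10%, margin B = 0.10, true difference 0, and z-values 1.96 and 1.65:

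n = (1.96 + 1.65)² × (0.10/0.10)² = 13.03

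This agrees with the stated 13 to the nearest whole number; unrounded z-values give 12.99. The formula contains no rate range, so the point below neither depends on it nor changes it.

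**2. Does another section close the gap?**

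| Section | Range | Pass limit | Covers 6 to below 8 BPM with a limit? |
|---|---|---|---|
| Primary Objective 1 | 6–40 BPM | none | no |
| Primary outcome 1 | none | none | no |
| Healthy, Effectiveness and Endpoint Analyses | none | none | no, descriptive |
| Healthy, Endpoints | 8–40 BPM | RMSE < 2 BPM | no |
| Pathologic, Endpoints | none | RMSE < 2 bpm, secondary | no |

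The pathologic criterion cannot stand in for the missing limit. Those subjects breathe normally throughout, and the note under Secondary Outcome Measures says respiration rate in that cohort is not a primary means of validation.

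**3. Does the justification support a bound of 8?** It rests on a 30-second window. On my reading, the 2 BPM figure is one breath in that window: 60/30 = 2 BPM. At 6 BPM the window holds 3 breaths and at 8 BPM it holds 4; one breath is worth 2 BPM in both cases. The argument is the same at either rate and gives no reason to start at 8.

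**4. Size of the gap.** In range terms it is 8 − 6 = 2 BPM out of 40 − 6 = 34 BPM, or 5.9%. The share of readings is more informative. The plan does not say which items enter the RMSE, so three cases are shown, with 20 subjects and one reading per item:

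- items 2–9: 20 × 8 = 160 readings; 20/160 = 12.5%
- items 1–9: 20 × 9 = 180 readings; 20/180 = 11.1%
- items 1–13: 20 × 13 = 260 readings; 20/260 = 7.7%

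The plan also does not say whether a reading is placed in the range by its paced or its measured rate. A reading in item 2 would have to run 2 BPM fast to reach 8, and one in item 3 more than 2 BPM slow to fall below it. If departures are slight, item 2 is out and item 3 is in under either rule.

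**5. Would extending the pooled range be a strong test at 6 BPM?** Take items 2–9 with equal numbers of readings per step, RMSE r on the seven other steps and x at 6 BPM. The pooled value is √[(7r² + x²)/8], which stays below 2 when x² < 32 − 7r².

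- r = 0.5: x < √30.25 = 5.5 BPM
- r = 0.8: x < √27.52 = 5.2 BPM
- r = 1.9: x < √6.73 = 2.6 BPM

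The values 0.5 and 0.8 are the ends of the preliminary RMSE range in the Sample Size Justification; 1.9 is an assumed value near the limit. If the device performs as in the preliminary data, a pooled 6–40 BPM RMSE would tolerate an error at 6 BPM of more than 5 BPM.

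**The case against.** The strongest reply is that this is a one-digit drafting slip with little effect on the result. The 6 BPM data are collected, and the planned analyses apply no range restriction, so they will be reported under a primary outcome. No section says that meeting the endpoint is by itself enough to declare Primary Objective 1 met. Step 5 also shows that adding the 6 BPM readings to a pooled RMSE would seldom change pass or fail. Finally, the reading counts assume one reading per item, although each measurement spans two positions and the analysis speaks of continuously collected pairs.

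Much of this is fair. What is missing is an acceptance limit, not an analysis, and the step from endpoint to objective is an inference. The counts are nominal, although the shares hold if every item yields equally many readings. A slip is possible, but the documents do not show which figure is in error, and the answer decides whether a whole step is scored. The weak effect of pooling is a reason to report RMSE by step; it does not make the two ranges agree.

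**Conclusion.** The concern holds. The objective starts at 6 BPM, the only healthy-cohort criterion starts at 8 BPM, and no section bridges or explains the difference. One of eight paced rates is collected but cannot count against the endpoint. Nominally that is 7.7% to 12.5% of readings, depending on which items enter the RMSE.

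The shares assume 20 subjects, equal readings per item and only slight departure from the paced rates. The inconsistency itself needs none of these assumptions. It does not invalidate the design or the sample size, but it should be settled before analysis because it determines either what is scored or what range can be claimed.

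**What to change.** Bring Primary Objective 1 and the healthy-cohort Endpoints to one range before analysis. There are two ways, and the choice is the sponsor's:

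- extend the criterion to 6–40 BPM, so that item 2 is scored; or
- narrow the objective to 8–40 BPM, give the reason, and label the 6 BPM data descriptive.

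Under either choice, state whether readings are assigned to the range by paced or by reference-measured rate, and which of items 1–13 enter the RMSE. Add a descriptive table of RMSE by paced step, with no further pass rule, so that the low end is visible whatever the pooled result.

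The cost is protocol wording and one table from data already being collected. Enrolment stays at 20. The price is either an endpoint that may be slightly harder to meet or a narrower claimed range.

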## **Relative Tidal Volume Endpoint Justification**

Tidal volume as measured by home-care ventilators have been shown to have a partial Spearman correlation of as low as 0.59 when compared against a reference data logger (Stagnara et. al, Respiratory Care, June 19, 2018). As this variability is deemed acceptable for ventilator products in the market that require greater accuracy for delivery of pre-set tidal volume, an accuracy of  $R^2$  value > 0.5 (R > 0.7) is deemed sufficient for its intended use.

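### The only acceptance limit for relative tidal volume, R² > 0.5, is blind to an offset or compressed response, so a CPM that substantially under-reports relative change can pass

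*Combined protocol and SAP*

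**What the plan says.** - **Objective.** Primary objective 2 is "Validate relative changes in tidal volume (rTV) derived by the CPM System".
- **Outcome measures.** These appear under an accuracy heading but are correlations only: "Correlation coefficient between reference device and test device within subjects" and "Average correlation coefficients across subjects for rTV for immediate and long timeframes between measurements".
- **Acceptance criterion, healthy cohort.** The Endpoints section has a line beginning "Relative Tidal Volume Precision has an", completed by R² > 0.5. The same section gives respiration rate an error limit, RMSE < 2 BPM.
- **Meaning of R².** The Relative Tidal Volume Endpoint Justification calls the criterion an accuracy and adds "R > 0.7) is deemed sufficient for its intended use". Since √0.5 = 0.707, R² here is a squared correlation.
- **Pathologic cohort.** The same R² > 0.5 appears under "Tidal Volume Accuracy (secondary", without an error or slope limit.
- **Sizing.** The healthy-cohort Sample Size Justification puts respiration-rate error at 2.5 to 4% and says "We expect the relative error of the tidal volume performance to be similar". It then takes a 10% worst-case SD and a 10% equivalence margin. The margin does not return as an endpoint.
- **Planned description.** Effectiveness and Endpoint Analyses provides for scatter plots with the line of identity and Bland-Altman plots, and states "The mean absolute error (MAE) and the root-mean-square error (RMSE) estimates of agreement will be calculated for each comparison".

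**The concern.** The objective is about relative change, so the natural question is whether a given proportional change in tidal volume appears as about the same proportional change in the CPM output. A squared correlation cannot answer it. It is unchanged if the CPM ratio is shifted or compressed linearly, and it falls only with scatter or non-linearity. Calling it precision in one section and accuracy in another hides this.

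The study is meant to support a 510(k) submission. A pass could be presented as validation of relative tidal-volume change when the criterion itself has established only that the two signals move together. Respiration rate has an error limit that a device can fail; relative tidal volume has none.

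**Working it through.** **The plan's own figure.** The sizing formula reproduces: n = (1.96 + 1.65)² × (0.10/0.10)² = 13.03, against the stated 13 (14 if rounded up; 20 are planned). The 2.5 to 4% also reproduces: 0.5/20 and 0.8/20.

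**Model.** Let x be true tidal volume divided by the subject's baseline, and let the CPM ratio be y = 1 + b(x − 1) + e. With b = 1, relative change is reproduced. With b = 0.2, y = 0.8 + 0.2x + e. Then

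expected R² = b²·Var(x) / (b²·Var(x) + SD(e)²),

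which exceeds 0.5 when SD(e) < b·SD(x). Without scatter R² is 1 for any b > 0.

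**Assumed inputs.** The exercise table gives tidal volumes mostly as inequalities, so I assume x = 0.7, 1.0, 1.4 and 1.8. The mean is 1.225, Var(x) = 0.6875/4 = 0.1719 and SD(x) = 0.415. The plan's 2.5%, 4% and 10% are used as the SD of e, in fractions of baseline.

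**Error when b = 0.2.** The readings are 0.94, 1.00, 1.08 and 1.16, so the errors are +0.24, 0, −0.32 and −0.64.
- RMSE = √[(0.0576 + 0 + 0.1024 + 0.4096)/4] = √0.1424 = 0.377 of baseline; scatter brings it to about 0.38 to 0.39.
- Mean difference = −0.72/4 = −0.18 of baseline. This is the closer comparison with the 10% sizing margin, which concerns a mean paired difference.

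**R² when b = 0.2.** b²·Var(x) = 0.04 × 0.1719 = 0.006875. The last three columns come from simulated studies of 20 subjects at four levels, with 5% jitter in the true values.

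| SD(e) | Formula R² | Simulated pooled R² | Pass, pooled R² | Pass, mean within-subject R² |
|---|---|---|---|---|
| 2.5% | 0.006875/0.007500 = 0.92 | 0.92 | about 100% | about 100% |
| 4% | 0.006875/0.008475 = 0.81 | 0.82 | about 100% | about 100% |
| 10% | 0.006875/0.016875 = 0.41 | 0.42 | about 15% | about 91% |

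Separate runs of the 10% row gave 14 to 17% and 91 to 92%. The break-even scatter is 0.2 × 0.415 = 0.083.

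**Dependence on the assumed levels.** For b = 0.2 at 4% scatter, expected R² is 0.69 for 400 to 800 mL, 0.86 for 350 to 1000 mL and 0.96 for 300 to 1500 mL. The pass rate is about 100% in each. At 10% scatter, pooled pass rates are about 0%, 50% and 100%.

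**A milder distortion.** With b = 0.5 a doubling reads as +50%. At the 0.7 to 1.8 ratios, b²·Var(x) = 0.0430, so even at 10% scatter expected R² = 0.0430/0.0530 = 0.81. Without scatter, RMSE is 0.5 × √0.2225 = 0.24 of baseline.

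**Can 20 subjects show the difference?** The mean within-subject slope of log(CPM ratio) on log(reference ratio) is about 1.00 for a faithful device. For b = 0.2 it is about 0.22 (not exactly 0.2, because the response is linear rather than a power law). Its SE at 5% scatter is about 0.015 if all subjects share the same response.

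**The case against.** **Scale-sensitive statistics are already planned.** The identity-line plot, Bland-Altman plot, MAE and RMSE would all make a strongly compressed response obvious. This stands, and it narrows the point: what is missing is an acceptance limit, not an analysis. A reader might infer that the plan never looks at magnitude; it does.

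**Impedance is uncalibrated, so gain is meaningless.** A pure gain error cancels when each reading is divided by the subject's own baseline, and it does no harm to relative change. A reader might infer that any mis-scaling is at issue. Only an offset or compression is, and that can be tested without calibration.

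**The example is hypothetical.** In 0.8 + 0.2x, 80% of the baseline signal does not vary with tidal volume. The protocol derives tidal impedance from breathing-related changes and gives no sign of so large an offset. That is fair: the example shows what the criterion lets through, not how the CPM behaves.

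**Such a device would not always pass.** This is also correct. At 10% scatter the result turns on the range of volumes and on whether R² is pooled or averaged within subjects, which the endpoint does not say. Response that varies between subjects would also lower the pooled pass rate.

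**Only tracking is intended.** The derivation section and the Background speak of tracking and trending, and correlation is a defensible, if weak, measure of that. But the hypothesis asks for accuracy and precision, and the justification calls R² an accuracy. If tracking is all that is meant, the claim should say so.

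**Conclusion.** The concern holds in this form: the sole acceptance limit for relative tidal volume cannot detect an offset or compressed response, so a CPM that substantially under-reports relative change can pass. In the illustration (b = 0.2, assumed ratios 0.7 to 1.8) it passes about 100% of the time at 2.5 to 4% scatter, with RMSE about 0.38 of baseline and a mean difference of −0.18, against a 10% sizing margin. At 10% scatter it passes about 15% of the time on pooled R² and about 91% on mean within-subject R².

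These figures rest on assumed tidal-volume levels, a linear response common to all subjects, and the plan's error figures read as scatter around that response. A reader might go further and infer that a compressed device always passes, or that the CPM is in fact compressed. The first fails at the 10% worst case with pooled R², and nothing in the documents supports the second.

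**What to change.** Keep R² > 0.5, state whether it is pooled or averaged within subjects, and add the following to the healthy-cohort analysis plan.

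1. For items 10 to 13 of the exercise table, express CPM and reference values as ratios to the subject's own baseline. Say whether item 1 or item 10 is the baseline, and how the Fowler and Supine halves are combined.
2. Report the already planned Bland-Altman statistics and RMSE on that ratio scale.
3. Report the mean within-subject log-log slope with a 95% CI over subjects, where 1 means relative change is reproduced. The slope does not depend on the choice of baseline.
4. Before the data are seen, state the limit on one of these that is needed to claim the size of relative change. The sponsor must justify it; the only related figure in the documents is the 10% sizing margin.
5. If the limit is not met, restrict the conclusion to tracking the direction of change. Stop describing R² as accuracy or precision.

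The cost is analysis-plan wording and one regression per subject on data already being collected. The downside for the sponsor is a possibly narrower claim.
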